continued access period	The period between study completion and end of trial during which patients on study therapy who continue to experience clinical benefit may continue to receive study therapy until 1 of the criteria for discontinuation is met.
CR	complete remission
CrCl	creatinine clearance
CRF/eCRF	case report form/electronic case report form Sometimes referred to as clinical report form: A printed or electronic form for recording study participants' data during a clinical study, as required by the protocol.
CRi	complete remission with incomplete blood count recovery
CRP	clinical research physician Individual responsible for the medical conduct of the study. Responsibilities of the CRP may be performed by a physician, clinical research scientist, global safety physician, or other medical officer.
CSF	cerebrospinal fluid
CT	computed tomography
CTCAE	Common Terminology Criteria for Adverse Events
CYP	cytochrome P450
DCSI	Development Core Safety Information (of Investigator's Brochure)
DDI	drug-drug interaction
DLET	dose-limiting equivalent toxicity
DLT	dose-limiting toxicity

DoR	duration of remission
ECG	electrocardiogram
ECOG	Eastern Cooperative Oncology Group
EDTA	ethylenediaminetetraacetic acid
EFS	event-free survival
ELISA	enzyme-linked immunosorbent assay
end of trial	End of trial is the date of the last visit or last scheduled procedure for the last patient.
Enroll	The act of assigning a patient to a treatment. Patients who are enrolled in the trial are those who have been assigned to a treatment.
enter	Patients entered into a trial are those who sign the informed consent form directly or through their legally acceptable representatives.
ERB/IRB	ethical review board/institutional review board
	A board or committee (institutional, regional, or national) composed of medical and nonmedical members whose responsibility is to verify that the safety, welfare, and human rights of the patients participating in a clinical trial are protected.
ESA	erythropoiesis-stimulating agent
F	oral absorption
FACT-Leu	Functional Assessment of Cancer Therapy-Leukemia
FHD	first-in-human dose
GCP	good clinical practice
G-CSF	granulocyte colony-stimulating factor
GI	gastrointestinal
GnRH	gonadotropin-releasing hormone
GSI	γ -secretase inhibitors
HD	heterodimerization domain
hERG	human ether-à-go-go-related gene
HNSTD	highest non-severely toxic dose
IB	Investigator's Brochure
IC₅₀	half-maximal inhibitory concentration
ICF	informed consent form

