6.3. Exploratory Objectives

The exploratory objectives of the study are as follows:

- to assess clinical utility of the NICD immunohistochemistry (IHC) assay as a potential companion diagnostic for LY3039478
- to evaluate biomarkers in tumor tissue, blood, plasma and cerebrospinal fluid (CSF), which may include, but not be limited to, NICD enzyme-linked immunosorbent assay (ELISA) (or an alternative validated method), gene expression, relevant to the study disease or safety, efficacy, and mechanism of action of LY3039478 and dexamethasone
- to explore PD effects of LY3039478 on biomarkers indicative of Notch activity
- to evaluate the CSF exposure of LY3039478

7. Study Population

Individuals who do not meet the criteria for participation in this study (screen failure) may be re-screened. Individuals may be re-screened up to 2 times. Each time re-screening is performed, the individual must sign a new informed consent form (ICF) and will be assigned a new identification number. Note that repeating laboratory tests during the 28-day screening period does not constitute rescreening.

Prospective approval of protocol deviations to recruitment and enrollment criteria (also known as protocol waivers or exemptions) is not permitted.

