8.3. Study Periods, Study Completion, and End of Trial

Terms used to describe the periods during the study are defined below:

- **baseline:** begins when the ICF is signed and ends at the first study treatment (or at discontinuation, if no treatment is given)
- **study period:** begins at the first study treatment and ends at study completion. The study period does not include the continued access period.
 - **study treatment period:** begins at the first study treatment and ends when the patient and the investigator agree that the patient will no longer continue study treatment. The date of this agreement is to be reported on the case report form (CRF) as the Date of Discontinuation from study treatment..
 - **postdiscontinuation follow-up period:** begins the day after the patient and the investigator agree that the patient will no longer continue study treatment.
 - **short-term follow-up:** begins the day after the patient and the investigator agree that the patient will no longer continue study treatment and lasts approximately 30 days.
 - **long-term follow-up:** begins the day after short-term follow-up is completed and continues until the patient's death or overall study completion.
- **continued access period:** begins after study completion and ends at the end of trial. During the continued access period, patients on study therapy who continue to experience clinical benefit may continue to receive study therapy until 1 of the criteria for discontinuation is met. The continued access period includes continued access follow-up.
 - **continued access follow-up:** begins 1 day after the patient and the investigator agree that the patient will no longer continue treatment in the extension period and lasts approximately 30 ± 6 days
- **study completion:** begins following the final analysis/evaluation of OS, as determined by Lilly. Investigators will continue to follow the Study Schedule for all patients until notified by Lilly that study completion has occurred.
- **end of trial:** occurs after study completion and after the last patient has discontinued study treatment and completed continued access period follow-up (if applicable).

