9.3. Method of Assignment to Treatment

9.3.1. Phase 1

Patients who enter the study during the Phase 1 portion will be assigned to receive LY3039478 and dexamethasone. Prior to enrollment into the study, an eligibility check must be conducted (for every patient) between the investigational site and the Lilly clinical research personnel, to confirm that the patient meets all enrollment criteria. Upon confirmation of eligibility, the sponsor will confirm the dose, cohort, and identification number assignment for each patient. No dose escalations (ie, to the next cohort) can occur without prior discussion and agreement with the responsible Lilly CRP.

9.3.2. Phase 2

Patients who enter the study during the Phase 2 portion will be randomized to receive either LY3039478 in combination with dexamethasone or placebo in combination with dexamethasone. Assignment to treatment groups will be determined by a computer-generated random sequence using an interactive web-response system (IWRS).

A dynamic allocation method, introduced by Pocock and Simon (1975) and extended for unequal treatment group sizes by Han et al. (2009), will be adopted to balance patient assignment between treatment arms, using a probability factor of 0.9, based on the following factors:

- age \leq 30 years versus $>$ 30 years
- T-ALL phenotype versus T-LBL, considered as 6 factors, representing the following 5 phenotypes of T-ALL:

TdT+, variable for all of the following: CD1a, CD2, CD3, CD4, CD5, CD7, CD8, CD34

- Pro-T-ALL: cCD3+, CD7+, CD1a-, CD2-, CD4-, CD8-, CD34+/-
- Pre-T-ALL: cCD3+, CD7+, CD1a-, CD2+, CD4-, CD8-, CD34+/-
- Cortical T-ALL: cCD3+, CD7+, CD1a+, CD2+, CD4+, CD8+, CD34-
- Medullary T-ALL: cCD3+, sCD3+, CD7+, CD1a-, CD2+, CD4+or CD8+, CD34-
- ETP T-ALL: Lack of CD1a and CD8 expression, weak CD5 expression with less than 75% positive blasts, and expression of 1 or more of the following myeloid or stem cell markers on at least 25% of lymphoblasts: CD117, CD34, HLA-DR, CD13, CD33, CD11b, and/or CD65
- response to last therapy: refractory/relapse within 1 year of last therapy vs. $>$ 1 year

The randomization parameter P will be set to 0.9 to maximize the benefit of the allocation procedure, whilst keeping treatment assignments unpredictable.

The IWRS will be used to assign bottles containing double-blind study drug to each patient. Site personnel will confirm that they have located the correct bottles by entering a confirmation number found on the bottles into the IWRS.

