**Table JJCB.6.1. Data Definitions and Rules**

Term	Definitions or Rule
Entered	Patients who have signed the informed consent document directly.
Screen failures	Patients who have signed informed consent, do not meet eligibility criteria and are not randomized.
Randomized/ Enrolled	Patients who have been assigned to study treatment and but may have not received any study treatment (LY3039478, LY3039478-matched placebo, or Dexamethasone).
Patients on therapy	Patients who have been randomized/enrolled to study treatment and have received at least 1 dose of study treatment (LY3039478, LY3039478-matched placebo, or Dexamethasone).
Study day	If assessment is on or after date of first LY3039478/ LY3039478-matched placebo dose then (date of assessment) – (date of first study treatment dose) + 1 If assessment precedes first treatment dose then (date of assessment) – (date of first study treatment dose) There is no study day 0. Study day 1 is the date of first dose and study day -1 is the day before the first dose.
Cycle day	If assessment is on or after date of first LY3039478/ LY3039478-matched placebo dose then (date of assessment) – (date of first study treatment dose in cycle) + 1 If assessment precedes first treatment dose then (date of assessment) – (date of first study treatment dose in cycle) There is no cycle day 0. Cycle day 1 is the date of first dose in the cycle and cycle day -1 is the day before the first dose.
Baseline	For change from baseline analysis, baseline value is defined as the last reported measure on or before the first dose date (or discontinuation, if no treatment is given).
Study treatment period	Time from treatment start to when the patient and the investigator agree that the patient will no longer continue study treatment. The date of this agreement is to be reported on the case report form (CRF) as the Date of Discontinuation from study treatment.
Post-discontinuation – short-term follow-up	The short term follow-up period begins 1 day after discontinuation of study treatment and lasts approximately 30 days (Visit 801).
Post-discontinuation – long-term follow-up	The long-term follow-up period begins 1 day after the short-term follow-up period (Visit 801) is completed and continues until patient's death or overall study completion

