### Secondary Endpoints:

- **Partial Response (PR)** is defined as the proportion of patients who achieved a best overall response of partial remission (PR), out of the total number of patients randomized in that arm.
- **Complete Remission (CR)** is defined as the proportion of patients who achieved a best overall response of complete remission (CR), out of the total number of patients randomized in that arm.
- **ORR and PR** is defined as the proportion of patients who achieved a best overall response of either complete remission (CR), incomplete remission (CRI) or partial remission (PR), out of the total number of patients randomized in that arm.

All of the above endpoints (ORR, PR, CR, ORR and PR) will also be calculated for those patients that cross-over in the Phase 2 part of the trial and receive LY3039478 plus dexamethasone after failure of placebo plus dexamethasone.

- **Overall Survival (OS)** is defined for all patients in the trial, and measured from the date of study enrollment to the date of death from any cause. OS duration is measured from the date of randomization to the date of death from any cause in the Phase 2 portion of the study. For each patient who is not known to have died as of the data-inclusion cutoff date for a particular analysis, OS will be censored for that analysis at the date of last contact prior to the

data inclusion cutoff date (contacts considered in the determination of last contact date include AE date, lesion assessment date, visit date, and last known alive date).

- **Relapse Free Survival (RFS)** is defined only for patients who achieve CR/CRI.

For T-ALL, RFS is measured from the date of attaining the leukemia-free state until the date of T-ALL relapse or death from any cause, whichever occurs first. Relapsed disease for T-ALL is defined as the reappearance of the blast in the blood or bone marrow (>5%) or any extramedullary site after achievement of a CR.

For T-LBL, RFS is measured from the time of occurrence of a disease-free state or attainment of a CR to disease recurrence or death as a result of lymphoma or acute toxicity of treatment.

For a patient who is not known to have relapsed or died by the end of study follow-up, observation of RFS is censored at the date of last contact prior to the data inclusion cutoff, at which an adequate assessment was completed, i.e. blood or bone marrow samples, CT-MRI or PET assessment.

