- **Event Free Survival (EFS)** is defined for all patients and measured from the date of entry on study. It is measured until treatment failure, relapse from CR, or death from any cause, whichever occurs first.

For T-ALL, treatment failure is defined by progressive disease, which is an increase of at least 25% in the absolute number of circulating or bone marrow blasts or development of extramedullary disease. For T-ALL patients with preexisting mediastinal disease, progressive disease is defined by a greater than 25% increase in the sum of the product of the greatest perpendicular diameters (SDP) of the mediastinal enlargement.

For T-LBL, treatment failure is defined as relapsed or progressive disease in protocol Table JJCB.10.1.

For a patient with none of these events before the end of study follow-up, observation of EFS is censored at the date of last contact prior to the data inclusion cutoff date, at which an adequate assessment was completed i.e. blood or bone marrow samples, CT-MRI or PET assessment. If the patient does not achieve a CR, EFS is defined as the point of treatment failure or death, whichever comes first.

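### Phase 2 EFS is counted from study entry (consent) while its own sensitivity rules and OS use randomization, and PR is missing from the list of adequate determinations

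*SAP*

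**What the plan says.** **Time origin.** SAP 6.11 defines EFS for all patients, "measured from the date of entry on study. It is measured until treatment failure, relapse from CR, or death from any cause". Protocol 10.1.3.1 (T-ALL) and 10.1.3.2 (T-LBL) use the same origin, and none of these places gives a separate origin for Phase 2. Protocol 4 defines the verb: "Patients entered into a trial are those who sign the informed consent form". SAP Table JJCB.6.1 defines Entered as "Patients who have signed the informed consent document directly". The baseline schedule in Protocol Attachment 1 lists informed consent under the Study Entry rows.

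For OS, the SAP does give a Phase 2 origin: "OS duration is measured from the date of randomization to the date of death from any cause". In SAP Table JJCB.6.2, SA 2 (when there is no earlier post-baseline assessment) and SA 3 (no adequate baseline) both censor EFS at the date of randomization.

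**Adequate assessments.** The EFS paragraph of SAP 6.11 censors event-free patients at the last contact with an adequate assessment, and defines adequacy by type of examination: blood or marrow sample, CT/MRI or PET. The next paragraph, on censoring rules for EFS and RFS, defines an adequate determination by response category: CR, CRi, SD, PD, relapsed or refractory. PR is not in that list.

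**Crossover.** The body text of Protocol 8.1 and SAP 5.1 ties crossover from placebo to treatment failure. Protocol 9.5 and the notes to the two design figures add relapsed or refractory disease as a further ground. Protocol 8.3 names relapsed or refractory disease. SAP 6.16 lists crossover without documented treatment failure as a protocol violation.

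**The concern.** A time-to-event endpoint needs one start date, and here the main definition and the sensitivity rules imply different ones. If EFS starts at consent, every randomized patient carries a stretch before randomization in which, by selection, no event occurred. That stretch enters the EFS medians and the 6- and 12-month Kaplan-Meier rates that SAP 6.11.3 prespecifies.

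Two inconsistencies follow. A patient whose first EFS event is death has an EFS time longer than the OS time, by the length of the gap. And SA 3 censors at randomization when there is no adequate baseline, which contributes zero follow-up only if randomization is the origin.

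The missing PR category puts two adequacy rules side by side. They can give different censoring dates for the same event-free patient, so the choice would fall to whoever programs the analysis.

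**Working it through.** **There is no plan figure to reproduce.** The documents state no EFS median, event count, hazard ratio or power.

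**Step 1: inputs for the time origin.**
- Landmarks: 6 and 12 months (SAP 6.11.3).
- Gap between consent and randomization: not stated. Protocol 7 mentions a screening period: "Note that repeating laboratory tests during the 28-day screening period does not constitute rescreening". The baseline schedule counts days back from Cycle 1 Day 1, so 28 days is taken as the upper end. Assumed range: 7 to 28 days.
- Median EFS from randomization: assumed 2, 3 or 4 months.

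**Step 2: formula.** With exponential EFS and a constant gap of d days, the rate read at t months from consent is exp(−(t − d/30.44) × ln 2 / median). For median 2, t = 6 and d = 28: 28/30.44 = 0.92, and exp(−5.08 × 0.693/2) = 17.2%. With d = 0 it is 12.5%.

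| Assumed median | Landmark | From randomization | Gap 7 d | Gap 14 d | Gap 28 d | Rise, 7 to 28 d (points) |
|---|---|---|---|---|---|---|
| 2 months | 6 mo | 12.50% | 13.54% | 14.66% | 17.19% | 1.0 to 4.7 |
| 3 months | 6 mo | 25.00% | 26.36% | 27.80% | 30.92% | 1.4 to 5.9 |
| 4 months | 6 mo | 35.36% | 36.79% | 38.29% | 41.46% | 1.4 to 6.1 |
| 2 months | 12 mo | 1.56% | 1.69% | 1.83% | 2.15% | 0.1 to 0.6 |
| 3 months | 12 mo | 6.25% | 6.59% | 6.95% | 7.73% | 0.3 to 1.5 |
| 4 months | 12 mo | 12.50% | 13.01% | 13.54% | 14.66% | 0.5 to 2.2 |

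The median moves by d/30.44: 0.23 months at 7 days, 0.46 at 14 and 0.92 at 28, in both arms.

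**Step 3: effect on the between-arm test.** A constant gap leaves the ranks unchanged, so it leaves the log-rank test unchanged. For a varying gap, 4,000 trials were simulated with 40 v 20 patients, control median 2 months, a gap uniform over 1 to 28 days and no censoring.
- Hazard ratio 1: rejection 5.4% from randomization v 5.3% from consent; 1.4% of trials changed verdict.
- Hazard ratio 0.5: 71.3% v 70.9%; 2.7% of trials changed verdict.

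**Step 4: the PR omission.** Protocol 10.1.1.2 assesses T-LBL every other cycle from the end of Cycle 2, about every 56 days. Take an event-free T-LBL patient with SD at day 56 and PR at day 112, then no further assessment.
- By type of examination: censored at day 112 or later.
- By the response list: day 112 does not count, so censored at day 56.
- Difference: at least 112 − 56 = 56 days, or 56/30.44 = 1.8 months of valid follow-up.

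The effect is mainly on T-LBL. Protocol 10.1.3.1 defines refractory T-ALL as not reaching CR, so a T-ALL PR could be coded refractory, which is on the list. Patients who later have an event are unaffected, and RFS is hardly touched because it covers only patients in CR or CRi.

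**Step 5: crossover.** Set side by side, the passages differ on whether refractory disease without progression is enough. For T-ALL the distinction is real: refractory means no CR, while the treatment failure counted in EFS is progression. The documents give no basis for estimating how often this would arise.

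**The case against.** **The intent is plain and the effect is small.** Protocol 9.3.2 uses the verb loosely: "Patients who enter the study during the Phase 2 portion will be randomized to receive either LY3039478". SA 2 and SA 3 also point to randomization. The shift is in the same direction in both arms, rests on assumed medians and gaps, and does not alter the test. At a 25% rate with 20 controls the binomial standard error is √(0.25 × 0.75/20) = 9.7 points, larger than any shift in the table. All of this stands, and it keeps the point minor. It does not remove the mismatch: the formal definitions say consent, and the shift is systematic whereas the standard error is not.

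**PR is a clerical slip.** Probably so, since SD is listed. The EFS paragraph can also be read as governing the main analysis, with the response list serving the sensitivity table. But the list is worded as a general rule for EFS and RFS, so both rules stand until it is corrected.

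**Stronger readings that a reader might infer, and why they fail.**
- *First dose as a third origin.* Protocol 8.3 says the study period "begins at the first study treatment and ends at study completion", but that defines a period, not entry. The worry that untreated randomized patients would have no start date depends on this strained reading.
- *Ambiguous consent date after re-screening.* Protocol 7 says "Each time re-screening is performed, the individual must sign a new informed consent form", but the same sentence assigns a new identification number, so the enrolled record has its own consent date.
- *Censoring at day 0 for a patient with only PR visits.* The response list gives no fallback date. Day-0 censoring appears only in SA 2 and SA 3, for other situations.
- *EFS has no rule for therapy after discontinuation, so crossover needs a new analysis.* SA 1 already censors EFS at transplant, which Protocol 12.2.5 counts as postdiscontinuation therapy. The ITT definition in Protocol 4, applied in SAP 6.11, already keeps patients who cross over in their randomized arm. A bias from crossover before progression is conditional and cannot be sized, and an extra analysis censoring at crossover would be a preference.

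**Conclusion.** The point holds as two definitional defects in a secondary endpoint. First, the EFS origin as written (consent) disagrees with the origin used in SA 2, SA 3 and Phase 2 OS (randomization). On assumed exponential EFS with medians of 2 to 4 months and a constant gap of 7 to 28 days, this raises 6-month EFS by about 1 to 6 points and 12-month EFS by about 2 points or less, in both arms, with the log-rank test essentially unchanged. Second, leaving PR out of the adequate determinations conflicts with the examination-based rule and can discard valid follow-up for event-free patients last seen in PR, mainly in T-LBL. How many patients that affects is unknown.

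The crossover conditions are inconsistent and must be reconciled, but this does not call for a change to the EFS analysis. The primary ORR analysis is unaffected. Severity: minor.

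**What to change.** 1. In SAP 6.11 and Protocol 10.1.3.1 and 10.1.3.2, state that Phase 2 EFS is measured from the date of randomization, as for OS and as SA 2 and SA 3 assume.
2. In the SAP 6.11 paragraph on censoring rules for EFS and RFS, add PR to the adequate determinations.
3. Reconcile the crossover conditions in Protocol 8.1 (text and figure note), 8.3 and 9.5 with those in SAP 5.1 (text and figure note) and 6.16. Which condition applies is for the sponsor to settle.

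The cost is wording only: no new data, visits or analyses. Protocol 12.2.1 lets minor clarifications of analysis methods be made in the SAP before the aggregate database is unblinded, so the SAP changes can be made at once, provided they come before that date.
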